## 5.2 STUDY POPULATION AND ENROLLMENT

Patients diagnosed with high-risk pulmonary embolism will be enrolled in this study. Subjects will be enrolled into one of three arms: the FlowTriever, Context, or Prior Therapy Arm. Sites participating in the FLAME study will enroll all subjects presenting with high-risk PE over the course of the study, regardless of their primary thrombus removal strategy, to ensure enrollment of all-comers to the study. Subjects will be concurrently enrolled in all arms as described below.

Enrollment in the Context Arm will continue until FlowTriever enrollment is completed, with a minimum enrollment of 1:1 subjects in each arm, and a maximum enrollment of 2:1 Context Arm to FlowTriever Arm subjects. Enrollment in the Prior Therapy Arm will be concurrent with the FlowTriever Arm of the study, and enrollment in this arm will cease when enrollment in the FlowTriever Arm is complete.

Individual sites will be limited to no more than 25% enrollment (maximum enrollment of 17 subjects) in the FlowTriever Arm of the study.

## 5.2.1 FlowTriever Arm Enrollment

Up to 71 subjects will be enrolled in the FlowTriever Arm. FlowTriever Arm subjects are defined as those subjects where FlowTriever is used as the Primary Treatment for pulmonary embolism.

An interim analysis is planned for the first 50 subjects enrolled into the FlowTriever Arm. Based upon the interim analysis (as described in **Section 7.4.3**), a decision will be made whether to continue enrollment.

## 5.2.2 Context Arm Enrollment

Subjects with high-risk pulmonary embolism who are treated with non-FlowTriever therapies (as the primary treatment for high-risk PE) will be enrolled concurrently with subjects in the FlowTriever Arm (this includes subjects initially presenting with low/intermediate-risk PE who are initially treated with anticoagulation alone and subsequently progress to high-risk PE. Enrollment in the Context Arm will continue until FlowTriever enrollment is completed, with a minimum enrollment of 1:1 subjects in each arm, and a maximum enrollment of 2:1 Context Arm to FlowTriever Arm subjects.

Context-Arm therapies may include but are not limited to; thrombolysis (either systemic or catheter directed), anticoagulation, surgical thrombectomy, and non-FlowTriever percutaneous thrombectomy.

## 5.2.3 Prior Therapy Arm Enrollment

Subjects presenting with low/intermediate-risk PE who receive advanced therapy but subsequently progress to high-risk PE in the same hospital setting/admission should be enrolled in the Prior Therapy Arm. Enrollment in the Prior Therapy Arm will be concurrent with the FlowTriever Arm of the study, and enrollment in this arm will cease when enrollment in the FlowTriever Arm is complete.

For the purposes of this study, advanced therapy for low/intermediate-risk PE is considered therapy beyond anticoagulation alone, including: thrombolysis (either systemic or catheter directed), surgical thrombectomy, and percutaneous thrombectomy.

FLAME Study (Protocol 20-001)

## 5.3 STUDY SITES

The FLAME Study will be conducted at up to 20 sites in the United States. Sites are selected based on a variety of factors including, but not limited to; experience with endovascular techniques, access to required facilities and equipment, sufficient and adequately trained personnel, and availability of potential subjects. The criteria used for determination will be documented.

Once activated to enroll in the FLAME study, sites should enroll **all** high-risk pulmonary embolism subjects into FLAME, regardless of the primary thrombus removal strategy. This will help ensure an unbiased enrollment of all-comers into the study.

## **5.4 ELIGIBILITY CRITERIA**

## 5.4.1 Inclusion Criteria

High-risk pulmonary embolism subjects must meet each of the following criteria to be eligible for enrollment:

- Age ≥ 18 years
- Treatment team determines pulmonary embolism is the cause of shock
- One or more of the following:
  - Systolic blood pressure <90 mmHg for at least 15 minutes, or drop of >40 mmHg in systolic blood pressure for at least 15 minutes, and/or
  - Need for vasopressor support, and/or
  - Resuscitation after cardiac arrest with <30 minutes of CPR and Glasgow Coma Scale >8.

## 5.4.2 Exclusion Criteria

High-risk pulmonary embolism subjects will be excluded from the study for any of the following criteria:

- Out of hospital cardiac arrest with Glasgow Coma Scale of ≤8
- Witnessed cardiac arrest with ongoing CPR >30 minutes
- Contraindication to anticoagulants, i.e. heparin or alternative
- Hematocrit <28%
- Platelets <25,000/µL
- INR >8
- Intracardiac thrombus and/or intracardiac clot in transit
- Known anaphylactic sensitivity to radiographic agents that cannot be pre-treated
- History of pulmonary hypertension with systolic pulmonary arterial pressure >70 mmHg
- Presence of chronic medical conditions with estimated life expectancy < 90 days (life-expectancy should not include the current pulmonary embolism and its treatment)
- Current participation in another drug or device treatment study that, in the Investigator's opinion, would interfere with participation in this study
- Subject is known to be COVID-19 positive at hospital admission (subject has active COVID-19)

# 6 FLAME STUDY CONDUCT

## 6.1 ENROLLMENT, STUDY ASSESSMENTS, AND PROCEDURES

## 6.1.1 Enrollment Logistics

Beginning at the point of site activation (approval to begin enrollment), all patients presenting to the hospital/ER with PE or who incidentally develop PE while in the hospital should first be reviewed to see if they have high-risk PE, and then assessed for eligibility for enrollment in the FLAME study. This will require a regular (approximately daily/weekly) chart and/or database review by site study personnel to ensure that all presenting high-risk PE subjects meeting criteria are enrolled.

Subjects who meet eligibility criteria for the study and have a primary thrombus removal strategy initiated, will be considered enrolled. The time of enrollment will be the initiation of the Primary Treatment Strategy for high-risk PE (the time of enrollment for patients in the Prior Therapy Arm will be the time of high-risk PE diagnosis).

Subjects who do not meet eligibility criteria or die before any anticoagulation or other thrombus removal strategy could be initiated will not be enrolled and will be considered screen failures. As such, screen failures will not be assigned a subject ID and will not be entered into the electronic data capture system (EDC, study database).

## 6.1.2 Patient Flow and Schedule of Assessments

Patient enrollment by study Arm study is provided in the Figure 4 flowchart. The Schedule of Assessments is included in Table 3.

Table 3:	Schedule of Assessments
----------	-------------------------

Assessment	Baseline	Procedure	Post-procedure through Hospital Discharge
Eligibility 	Х		
Medical History 	Х		
Pre-procedure presentation and status 	Х		
Anticoagulation 	Х	Х	Х
Thrombolytic Therapy 	Х	Х	Х
Primary Treatment Plan Decision for high-risk PE 	Х		
Primary Treatment Initiated for high-risk PE 		Х	
Bailout therapies for high-risk PE 		Х	Х
Clinical Deterioration 		Х	Х
Major Bleeding Events 		Х	Х
Adverse Events 		X	X
Discharge details			Х

Data used to determine eligibility include pre-treatment data only.

Data collected for subject Medical History include pre-treatment data only.

Signs and symptoms of high-risk PE beginning should be reviewed for eligibility. Data should also be collected for subjects first presenting with low/intermediate-risk PE who progress to high-risk PE in the same hospital setting/admission, including any treatment given to treat the low/intermediate-risk PE.

Anticoagulation and thrombolytic therapy administration are not required, but if administered, detailed data will be

collected including drug name, dosage, start and stop dates/times, route, and reason for administration.

The Primary Treatment plan for treating the high-risk PE will be documented including the date and time that the Primary Treatment plan was decided.

The date and time the Primary Treatment for thrombus removal is initiated will be documented. The patient is considered enrolled at the time the Primary Treatment for high-risk PE is initiated (the time of enrollment for patients in the Prior Therapy Arm will be the time of high-risk PE diagnosis).

Any bailout therapies for thrombus removal applied after initiation of the Primary Treatment therapy through hospital discharge will be documented and subsequently adjudicated by the CEC. See Section 6.1.4.1 for details.

Clinical deterioration occurring after initiation of the Primary Treatment therapy through hospital discharge will be documented and subsequently adjudicated by the CEC. See Section 6.1.4.2 for details.

Major bleeding events occurring from the time of initiation of the Primary Treatment therapy through hospital discharge will be documented as adverse events and subsequently adjudicated by the CEC. See Section 6.1.4.3 for details. Only Adverse Events (AEs) related to the subject's PE condition and its treatment should be reported in the FLAME study.

## 6.1.3 Baseline

## 6.1.3.1 Waiver of Informed Consent in Emergency Research

Patients with high-risk pulmonary embolism are, by definition, unstable with a life-threatening condition and require emergent treatment. Currently, patients with high-risk pulmonary embolism suffer from 30-40% acute mortality , necessitating the analysis of current treatments for this high-risk patient population.

The FLAME registry study will not dictate use of any specific therapy for the pulmonary embolism. Treatment will be at the discretion of the physician caring for the patient, utilizing standard of care treatment, and the data surrounding the treatment decision and patient outcomes through hospital discharge will be collected via retrospective chart review in the FLAME registry. Per the Department of Health and Human Services criteria for a waiver of consent in research for non-FDA regulated studies (45 CFR 46.116(d)), the FLAME study will include a waiver of consent for the following reasons (as listed in the regulation):

## 1. The research involves no more than minimal risk to the participants.

The FLAME observational registry will not dictate use of any specific therapy for the pulmonary embolism. Treatment will be at the discretion of the physician caring for the patient, utilizing all available standard of care therapies for pulmonary embolism, and the data surrounding the treatment decision and patient outcomes through hospital discharge will be retrospectively collected in the FLAME registry, **therefore additional risks are not introduced specific to the study**.

The only known risk to participants is the possible loss of confidentiality which has been guarded against by the following:

- Data surrounding the treatment and patient outcomes through hospital discharge will be anonymized, re-identified with a study-specific subject ID, and collected for analysis.
- Only the study site (Investigators and research staff) will have access PHI, providing an
  acceptable risk/benefit ratio for data collection and analysis activities performed for the
  study.
- Access to the study database where anonymized data is entered is password protected and compliant with 21 CFR 11, Electronic Records.
- Access to study data will be limited to hospital research and Sponsor personnel.

Evaluating subject records fits the definition of minimal risk.

## 2. The research could not practicably be carried out without the waiver or alteration.

As noted above, patients in this high-risk population suffer from 30-40% acute mortality, and treatment of these patients would occur regardless of the research. In order to carry-out credible and representative research in this population, all patients presenting with high-risk pulmonary embolism should be included in the results, including those who expire in the acute period following their pulmonary embolism. This research could not be practicably carried out **without** the waiver of consent to ensure proper accounting for patient mortality.

This study is a non-interventional, data collection registry. As described above, patients with high-risk pulmonary embolism are, by definition, unstable with a life-threatening condition requiring emergent treatment. Patients with high-risk pulmonary embolism are unable to consent for data collection due to their medical condition. There is no reasonable way to prospectively identify potential eligible subjects and the data surrounding the treatment decision and patient outcomes will be collected in the FLAME registry via retrospective chart review by site research staff.

3. If the research involves using identifiable private information or identifiable biospecimens, the research could not practicably be carried out without using such information or biospecimens in an identifiable format;

Identifiable private information **will not** be collected in the FLAME study. As described above, data surrounding the treatment and patient outcomes through hospital discharge will be anonymized, re-identified with a study-specific subject ID, and collected for analysis. Only the study site (Investigators and research staff) will have access PHI, providing an acceptable risk/benefit ratio for data collection and analysis activities performed for the FLAME study.

## 4. The waiver or alteration will not adversely affect the rights and welfare of the participants.

As the study is collecting de-identified real-world treatment data after the patients have already left the hospital, and the study is not prescribing the intervention or therapy, the FLAME study will not adversely affect the rights and welfare of the participants.

# 5. Whenever appropriate, the participants will be provided with additional pertinent information after participation.

This study is non-interventional and thus providing information to patients is not likely. However, if there were information that needed to be provided to the subject, we would work with the IRB to approve the correspondence to be provided to the subject.

## 6.1.3.2 Eligibility

Subjects will be enrolled by retrospective chart review. This is especially important for subjects enrolled in the Context and Prior Therapy Arms, to help eliminate the potential for enrollment bias. Once a site is activated to enroll in the FLAME study, ALL patients presenting with suspected PE should be assessed for high-risk PE status, and potential enrollment into the FLAME study.

All inclusion criteria must be met, and none of the exclusion criteria can be met for enrollment into the study (for all arms). All eligibility criteria are listed in **Section 5.4**. Subjects will be considered enrolled when the Primary Treatment for thrombus removal is initiated for high-risk PE (the time of enrollment for patients in the Prior Therapy Arm will be the time of high-risk PE diagnosis).

Patients not meeting eligibility criteria for the study will be considered Screen Failures, will not be enrolled, and are not entered into the EDC system.

## 6.1.4 Treatment

The treating physician should document what the intended initial treatment strategy was for high-risk PE (referred to as the Primary Treatment). Subjects with the Primary Treatment being FlowTriever will be enrolled into the FlowTriever Arm of the study. Subjects with the Primary Treatment being non-FlowTriever therapy will be enrolled into the Context Arm of the study. Subjects presenting with low/intermediate-risk PE who receive advanced therapy but subsequently progress to high-risk PE in the same hospital setting/admission should be enrolled in the Prior Therapy Arm.

Details of the treatment of PE (Primary Treatment, Bailout measures, Clinical Deterioration, and Major Bleeding) will be collected.

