## 5.1 ENDPOINTS

## 5.1.1 Primary Endpoint

The primary endpoint is the in-hospital composite endpoint of all-cause mortality, bailout to an alternative thrombus removal strategy, clinical deterioration, and major bleeding (BARC 3b/3c/5a/5b definition). This will be assessed in the FlowTriever Arm compared to a performance goal. A description of the analysis methods is provided in **Section 7**. Definitions of each component of the composite primary endpoint are provided in **Table 1** below.

Subjects enrolled in the Context Arm will be analyzed separately from the endpoint analysis utilizing descriptive methods.

Primary Endpoint Definitions	Bailout to an alternate thrombus removal strategy	Need for mechanical circulatory support or another thrombus removal strategy after the primary treatment strategy was initiated. The additional treatment strategy was not an a priori part of the original treatment plan (conceived beforehand). All bailout events will be adjudicated by the CEC.
	Clinical Deterioration	Need for CPR

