## 6.3 CLINICAL EVENTS COMMITTEE (CEC)

A Clinical Events Committed (CEC) will be utilized in this study for the purposes of adjudicating the primary and secondary endpoints. Site-reported safety and outcome data will be provided to the CEC for review and adjudication of the following items for all FlowTriever and Context Arm subjects enrolled in the study:

- Classification as a Serious Adverse Event (SAE)
- Determination of relatedness
- Assessment of severity
- Assessment of endpoint criteria

Adjudication will be conducted according to the FLAME CEC Charter.

(Note that the primary endpoint will only be analyzed for subjects in the FlowTriever Arm of the study, but the CEC will adjudicate events for subjects enrolled in the Context Arm of the study as well)

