## 7.4 ENDPOINT ANALYSIS

## 7.4.1 PRIMARY ENDPOINT ANALYSIS

The primary endpoint is the in-hospital composite endpoint of all-cause mortality, bailout to an alternative thrombus removal strategy, clinical deterioration, and major bleeding (BARC 3b/3c/5a/5b definition) from the FlowTriever Arm. The rate of the composite endpoint is expected to be 18% and compared with performance goal of 32%:

H0:  $P_S \ge Performance Goal_s versus H_A: P_S < Performance Goal_s$ 

where Ps is the proportion of subjects with in-hospital composite endpoint and Performance Goals is the performance goal of proportion of subjects with in-hospital composite endpoint derived from previous publications and expert opinions on subjects who were non-FlowTriever treatments.

The one-sided binomial's proportion test with normal approximation would be used at a one-sided  $\alpha$  = 0.05. Primary endpoint analysis can be carried out at interim analysis and/or final analysis stage.

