## 7.4.3 INTERIM ANALYSIS

The interim analysis population will be N = 50 enrolled subjects in the FlowTriever Arm with adjudicated in-hospital composite endpoint. Primary endpoint analysis method in **Section 7.4.1** will be used on the interim analysis population to decide whether the study should be stopped early due to achieving early decision rule based on the primary endpoint. The |z - score| threshold is 2.031, which translates to inhospital composite endpoint proportion being  $\leq$  0.186. Therefore, having  $\leq$  9 in-hospital composite endpoint events out of N = 50 may qualify for stopping the study early and conclude achieving significant difference from performance goal = 32% (see Table 9).

Secondary endpoint analysis may be conducted in a descriptive fashion without hypothesis testing, therefore not spending any Type I error ( $\alpha$ ).

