5.1. Sample Size

The sample size of the FlowTriever arm is calculated using a two-stage group sequential design, where the FlowTriever arm is expected to have a rate of in-hospital composite endpoint of all-cause mortality, bailout to an alternative thrombus removal strategy, clinical deterioration, and major bleeding (BARC 3b/3c/5a/5b definition) of 18%. The rate of the FlowTriever arm composite endpoint is compared with the historical performance goal of 32%, based on meta-analysis results shown in **Table** . A one-sided binomial proportion's test with normal approximation is used against the performance goal with a power of 80% and a one-sided α = 0.05; O'Brien Fleming boundary was implemented where the first stage, or interim analysis, is planned at N = 50 subjects enrolled and consequently arriving at the second stage, or final analysis, with N = 71 subjects as shown in **Table** .

Table 3: Sample Size 2-stage Group Sequential Design

Analysis Stage	N	Z-score Threshold	P-value Threshold	FT Event proportion	Significant event number
Interim	50	-2.0311	0.0211	0.186	≤9.3
Final	71	-1.7116	0.0435	0.225	≤16.0

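### The bailout exemption depends on what was planned beforehand, but nothing requires the plan record to pre-date treatment, so an added thrombus-removal strategy can be called planned with hindsight

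*Protocol*

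**What the plan says.** The bailout definition in Protocol 5.1.1, repeated in Protocol Table 10 and SAP 2.2, covers circulatory support or another thrombus-removal strategy used after the primary strategy has begun. It adds a condition on intent: "The additional treatment strategy was not an a priori part of the original treatment plan".

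On how the plan is recorded:

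- Protocol 6.1.4: "The treating physician should document what the intended initial treatment strategy was for high-risk PE". No deadline is given.
- Protocol Table 3 lists the plan decision as a Baseline item, and footnote 5 asks for the date and time of the decision.
- Protocol Table 10 defines the Primary Treatment Strategy as one settled by the team before treatment starts, and documented.

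On when data are collected, Protocol 6.1.3.2 states: "Subjects will be enrolled by retrospective chart review". The waiver justification in 6.1.3.1 (criterion 4) describes the study as "collecting de-identified real-world treatment data after the patients have already left the hospital".

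On who decides, Protocol 6.1.4.1 gives classification of bailout to the CEC. Its input is described in 6.3: "Site-reported safety and outcome data will be provided to the CEC for review and adjudication". Adjudication follows a CEC Charter that is not among the documents.

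Protocol Table 4 has a separate row for mechanical thrombectomy, which includes FlowTriever. That row defines bailout by sequence, meaning what was needed once the percutaneous approach had begun. It exempts circulatory support only if the support was both planned and placed before thrombectomy, and it exempts adjunctive lysis by route and dose limit. The note on circulatory support breaks off in the text available for this review, and nothing is held against the plan for that.

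**The concern.** Of the four components, bailout is the one whose general definition turns on recorded intent. Two patients with the same sequence of treatments can be classified differently according to what the record says was planned. That is sound if the record was made before anyone knew how treatment went. The documents time the decision, not the entry, so a decision time can be written down later by someone who knows what was added and how the patient did. The CEC then adjudicates from what the site supplies.

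The study is open-label, and the FlowTriever Arm is tested against a fixed 32% goal. An error in classifying that arm is therefore not offset by a similar error in a comparator. Ordinary hindsight is enough to produce it; no intent to mislead need be supposed. The expected direction is towards fewer events and an easier success.

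**Working it through.** **Inputs.** Goal p0 = 0.32 and expected rate 0.18 (Protocol 7.4.1). Design: "power of 80% and a one-sided α = 0.05" (SAP 5.1). Interim at N = 50: "The |z - score| threshold is 2.031" (Protocol 7.4.3), with success at 9 or fewer events. Final at N = 71: z threshold -1.7116, stated as 16.0 or fewer events (Protocol Table 8, SAP Table 3).

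**Reproducing the plan's figures.** Boundary proportion = p0 - z × sqrt(p0(1 - p0)/N).

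- Interim: 0.32 - 2.0311 × sqrt(0.2176/50) = 0.32 - 2.0311 × 0.06597 = 0.1860, or 9.30 events. This matches.
- Final: 0.32 - 1.7116 × sqrt(0.2176/71) = 0.32 - 1.7116 × 0.05536 = 0.2252, or 15.99 events. This matches the stated proportion, but 15.99 is just below 16.
- Treating the two z statistics as bivariate normal with correlation sqrt(50/71), overall alpha is 0.0501. Power is 80.3% using the null variance.

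**Sensitivity to one subject.** z = (x/N - 0.32)/sqrt(0.2176/N).

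| Count | z | Threshold | Result |
|---|---|---|---|
| 9/50 | -2.122 | -2.0311 | passes |
| 10/50 | -1.819 | -2.0311 | fails |
| 15/71 | -1.964 | -1.7116 | passes |
| 16/71 | -1.710 | -1.7116 | passes on the stated count, just misses on z |
| 17/71 | -1.455 | -1.7116 | fails |

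Because 16/71 is ambiguous, both final limits are carried forward.

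**Effect on false success.** Suppose the true composite rate is 32%, and m percentage points of subjects whose only event is a bailout are recorded as having had a planned addition. The recorded rate is then p = 0.32 - m/100. With X binomial (50, p), Y binomial (21, p) and final limit b,

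P(success) = P(X ≤ 9) + sum over x ≥ 10 of P(X = x) × P(Y ≤ b - x).

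| m (assumed) | b = 16 (stated count) | b = 15 (implied by z) |
|---|---|---|
| 0 | 5.9% | 3.9% |
| 1 | 8.3% | 5.5% |
| 2 | 11.3% | 7.7% |
| 3 | 15.1% | 10.5% |
| 5 | 25.3% | 18.6% |

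The documents give neither a relabelling rate nor the frequency of bailout-only subjects, so m is shown as a range.

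**Which additions are exposed in the FlowTriever Arm.** Three cases follow from setting the general definition beside the mechanical row of Table 4.

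1. Circulatory support started after thrombectomy began does not meet the Table 4 exemption as written, whatever the plan is said to have been. The general definition has no placement-time condition, and it is the only one the SAP carries. The two texts therefore differ here.
2. Adjunctive lysis within the Table 4 exemption is classified by route and dose, not by intent.
3. Any other added thrombus-removal strategy is a bailout under the Table 4 sequence wording, but is exempt under the general definition if it was planned. This is the main route by which a late plan entry could remove an event.

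**The case against.** The controls in the plan are real. The plan decision is a dated and timed Baseline item, the strategy is by definition settled before initiation, and the CEC, not the site, classifies bailout. Chart review by research staff draws on hospital records, not on operator recall. Protocol 6.1.1 expects charts to be reviewed about daily or weekly, source records are open to verification (6.10.2), and eCRF changes carry an audit trail (6.10.1). These controls narrow the gap. They do not close it, because none requires the plan entry to pre-date treatment, and an audit trail dates the eCRF entry, not the source note behind it.

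A reader might infer several stronger things that the documents do not support:

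- *Any rescue can be relabelled, including later ECMO or step-up lysis.* The mechanical row of Table 4 largely prevents this in the tested arm, subject to reconciliation with the general definition.
- *A relabelled rescue always leaves the endpoint.* The subject still counts if there is a death, a qualifying deterioration or a major bleed, and rescued patients may well have one.
- *The error can only favour the device.* A genuinely planned combination with poor notes could be counted as a bailout. Downward bias is the expected direction, not the only one.
- *The CEC has no rule for a missing plan.* The Charter is unseen. It can only be said that the protocol and SAP state none.
- *Bailout will dominate the FlowTriever events because its pooled rate is 30.3%.* That figure is 28/92 from non-FlowTriever literature cohorts (95% CI 15.5% to 50.7%), while the plan expects 18% for the whole composite.

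It is also true that one subject near a count threshold matters for any component. What is particular to bailout is that its classification can rest on a statement of intent entered after the event.

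**Conclusion.** The concern stands in a limited form. A primary-endpoint event can depend on prior intent, and neither the protocol nor the SAP requires that intent to be on record before treatment begins. In the FlowTriever Arm this concerns mainly added thrombus-removal strategies, in subjects with no other component event. One such subject can move the interim result across its boundary. Two hidden percentage points at a true rate of 32% would roughly double the chance of a false success: 5.9% to 11.3% with the stated final count, or 3.9% to 7.7% with the count the z threshold implies. The arithmetic is exact, but the relabelling rates are assumptions, and the true effect could be nil if the CEC Charter or site practice already demands contemporaneous proof. The sample size and boundaries are not in question here. The change is worth making because it is cheap and protects the endpoint most open to hindsight.

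**What to change.** 1. In Protocol 6.1.4, Table 4 and the CEC rules, state that the a priori exemption must be supported by a source-record entry time-stamped before Primary Treatment initiation and naming the additional strategy. A response-team note, consult, order or procedure consent would serve.
2. Send that page to the CEC for every subject with an added therapy, in both adjudicated arms (FlowTriever and Context).
3. Pre-specify in the SAP a sensitivity analysis of the primary endpoint that counts every added strategy without such an entry as a bailout. Making that the primary rule is debatable in emergency care, where a missing note may reflect urgency and not a missing plan.
4. Reconcile the general definition (Protocol 5.1.1 and Table 10, SAP 2.2) with the mechanical row of Table 4, so that both documents classify circulatory support and added strategies by the same test.
5. While editing, reconcile the final count of 16 with the z threshold of -1.7116.

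Cost: a paragraph in the protocol and the CEC rules, one extra SAP analysis, and one source page per affected subject. The downside is a possibly less favourable rate, chiefly in the sensitivity analysis, where some genuinely planned combinations with no prior note will count as events.
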